6.3 Visit 3 -1 Day Follow-up

Subjects will be seen in clinic or contacted by phone or by teleconference, per the subject's preference, the day following GAE or sham procedure (+3 days). As most complications of the procedure will be evident within this time period, this visit is to evaluate for early AE's. If an AE is suspected based on change in pain scores or functionality, an appropriate work-up will be performed which may include MRI.

6.4 Visit 4 – 2 Week Follow-Up

Patients will be called after 2 weeks to assess any adverse events, such as persistent pain.

6.5 Visit 5a and 5b - 1 Month Follow-Up

Subjects will be seen in clinic or contacted by phone or by teleconference, per the subject's preference, 30 +/- 7 days following GAE or sham procedure. The WOMAC questionnaire and VAS pain score will be completed and subjects will be evaluated for possible adverse events. An MRI of the treated knee will be acquired for those subjects who underwent GAE*. Subjects will also provide an update about the necessity/frequency of pre-established conservative therapies.

For those subjects who do not report improvement in symptoms or worsening, and are in the placebo arm, they will be unblinded and offered to undergo the geniculate artery embolization (Arm C) and then followed at similar follow-up intervals to 12 months (24 hours, 2 weeks, 1 month, 3 months, 6 months, and 12 months).

*MRI is only scheduled at one month in order to evaluate for non-target ischemic injury. These types of injuries will become apparent as early as 24 hours after embolization. Infarcted tissue will still be detectable at one month. Based on our experience with embolization in other areas, it is thought extremely unlikely that new ischemic injury related to the procedure will develop after the one-month follow-up. Additionally, findings that would be detected on later scans may be unrelated to the procedure and confound the data.

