3.1 General Design

This will be a single-blinded randomized-controlled study of GAE versus placebo in a small population with knee pain secondary to arthritis to determine safety and efficacy. After IRB approval of a written informed consent and over, approximately a 24 month duration, N=21 subjects will be recruited. Only subjects ≥ 40 years will be screened for study recruitment. Subjects will be randomized in a 2:1 ratio of GAE:Placebo and will be blinded from study treatment (see flow chart below). The placebo procedure will be a diagnostic angiogram of the knee, without embolization. Appropriate measures will be taken to ensure patients and nursing staff caring for the patient are blinded to assignment. Each patient will be told at the time of recruitment that they may be randomly assigned to sham, but if after 1 month they have not had symptom improvement, their assigned procedure would be revealed and, if they had undergone a sham procedure, they will be allowed to proceed with embolization. This second procedure should be shorter than a complete angiogram and embolization, as the detailed angiogram will not need to be repeated, and therefore both arms will have similar total radiation dose.

Clinical procedures and evaluations will consist of a preoperative screening assessment to determine if the potential study subject meets the inclusion and exclusion criteria, enrollment, surgical procedure for geniculate artery embolization, and follow-up visits at 24 hours, 2 weeks, 1, 3, 6, & 12 months. An MRI will be performed after the 1-month visit in those patients who underwent embolization to detect a change in synovial vascularity and to exclude complication.

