3.2 Primary Study Endpoints

1. Overall efficacy of treatment as determined by a minimal clinically significant reduction in global Western Ontario and McMaster University

Osteoarthritis Index (WOMAC) questionnaire scoring of 16% at 1 and 6 month follow-up.

2. Minimal clinically important decrease of 15% on the pain VAS at 1 or 6 months follow-up.

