5.5 Blinding of Study

Following randomization, efforts will be made to blind the subject to the study procedure. Patients will not be informed to their treatment or placebo arm. As the procedures of a diagnostic angiogram and embolization are similar (femoral artery access, angiogram, post-operative care), the subject will inherently not know if he/she received the treatment or placebo. The post-operative staff caring for the patient will not be informed as to the treatment the patient received. Datasets for each arm will be presented for analysis by statistician labeled as treatment arm (i.e. A, B or C).

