6.1 Screening Visit (Visit 1)

Potential enrollees will first be identified and will undergo a standard knee OA work-up to include history and physical exam with emphasis on specific site of knee tenderness. The Western Ontario and McMaster University Osteoarthritis Index (WOMAC) questionnaire will be administered to assess difficulty as a result of pain, stiffness and overall decreased function secondary to knee pain in the past week.

Current pain will also be assessed using a visual analog scale (VAS). A knee radiograph will be obtained and evaluated using the Kellgren-Lawrence grading scale. A baseline knee MRI will also be acquired to evaluate for concomitant pathology as part of routine orthopedic evaluation. If the patient previously had an MRI for clinical care that can be obtained from his/her medical record and used for the purposes of this study.

If a patient qualifies to be a subject in the study based on the inclusion and exclusion criteria listed in section 4.3 and 4.4, the local study coordinator, investigator or designee will provide the candidate with a copy of the approved informed consent. Written informed consent will be obtained if appropriate. If the patient wishes to take more time to review the study before enrolling, he/she may complete the consent process at the beginning of the next visit, prior to the study GAE procedure. Those candidates who are disqualified from study entry will be logged into the Screening Log with a reason for no study entry. A copy of the consent will be provided to the subject and the original filed in the study files.

Patients will be randomized at this point according to the schema created prior to the commencement of the study.

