6.6 Visit 6a and 6b - 3 Month Follow-Up for blinded subjects

Subjects will be seen in clinic or contacted by phone or by teleconference, per the subject's preference, 90 +/- 10 days following GAE or sham procedure. The WOMAC questionnaire and VAS pain score will be completed and subjects will be evaluated for possible adverse events. Subjects will also provide an update about the necessity/frequency of pre-established conservative therapies. If an AE is suspected based on change in pain scores or functionality, an appropriate

work-up will be performed which may include MRI.

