8.2 Statistical Methods

The primary study endpoints, WOMAC and VAS scores, will be collected at baseline, 1 month follow-up, 3 month follow-up, and 6 month follow-up. Mean WOMAC and VAS scores will be reported at baseline, 1 month follow-up, 3 month follow-up, and 6 month follow-up, along with associated confidence intervals.

We will address the primary study endpoints by modeling each clinical outcome using random coefficient modeling. The clinical outcomes will be modeled as a linear function of time. We will allow a random intercept and slope that is dependent on treatment, so that each patient will have their own trajectory of pain over time. No additional covariates will be included in the model. We will employ a compound symmetric R-side covariance structure to account for dependencies arising from observations from the same patient. Random coefficient models are robust to missing values only require data to be MAR (and not the stronger assumption of MCAR), so that presence of missing values will not invalidate our conclusions.

We will compute predicted means, as well as the estimated difference in predicted means, at 6 months for both WOMAC and VAS; these will be derived from the population-averaged trajectories (i.e. fixed effects). We will test the H₀: $\mu_{sham, 6}$ months - $\mu_{GAE, 6 \text{ months}} = 0$ versus the one-sided alternative hypothesis H_a: $\mu_{sham, 6}$ months - $\mu_{GAE, 6 \text{ months}} > 0$ using a Wald test. Both primary study endpoints will be evaluated by considering significance of the p-value (p < 0.05) along with the percentage predicted mean difference with respect to the clinically relevant differences (16% for WOMAC and 15% for VAS). Both these factors will be taken in tandem as evidence to suggest GAE treatment efficacy. Primary endpoints will be assessed only at one time point, so that adjustment for multiple comparisons is not necessary since the evaluation of the primary endpoints for WOMAC and VAS each consists of only one statistical test. Non-significance of the p-value for this test will be considered inconclusive evidence against the null hypothesis. Variance components, including the intraclass correlation coefficient, will also be reported for each model. All analyses will use SAS version 9.4 (SAS Institute, Inc., Cary, NC).

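### The 1-month MRI scheduled for GAE subjects alone, together with the 1-month unblinding rule, may disclose the arm before the 6-month efficacy test

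*Combined protocol and SAP*

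**What the plan says.** **The MRI.** Section 6.5 (1-month visit): "An MRI of the treated knee will be acquired for those subjects who underwent GAE". Section 3.1 has the same rule with different timing: "An MRI will be performed after the 1-month visit in those patients who underwent embolization". Section 6.5 also says "MRI is only scheduled at one month in order to evaluate for non-target ischemic injury".

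**Other MRIs.** At screening (Section 6.1), "A baseline knee MRI will also be acquired to evaluate for concomitant pathology"; an existing clinical scan may be used instead. If an adverse event is suspected, Sections 6.3, 6.6 and 6.8 allow an unscheduled one in either arm ("work-up will be performed which may include MRI"). Sham subjects who cross over are scanned at visit 9c (Section 6.11), when they already know their arm.

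**Blinding.** Section 5.5 says "Patients will not be informed to their treatment or placebo arm". It rests subject blinding on the similarity of angiography and embolization and does not mention the MRI. The titles of Sections 6.6 and 6.8 still describe the 3- and 6-month subjects as blinded.

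**Planned unblinding.** Under Sections 3.1, 5.2 and 6.5, a sham subject without improvement at 1 month is told the arm and offered embolization. Section 5.2 limits the disclosure to sham subjects.

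**The test.** Section 8.2 compares predicted means "at 6 months for both WOMAC and VAS", one-sided at 0.05. Section 3.2 also names 1 month, for example "Minimal clinically important decrease of 15% on the pain VAS at 1 or 6 months follow-up".

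**The concern.** WOMAC and VAS are both reported by the subject, and a sham arm is there to balance expectation between arms. That balance lasts only while subjects cannot tell which procedure they had. Here a visible event depends on the arm and comes well before the tested time point. It is a conspicuous one: the 1-month visit may be done by phone or teleconference, but a scan requires attendance. A GAE subject who learns that only embolized subjects are scanned can identify the arm, and a sham subject can draw the opposite conclusion from not being scanned.

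The 1-month rule adds a second route. Non-improving sham subjects are told outright. Because Section 5.2 discloses the arm only to sham subjects, a non-improving GAE subject who is told nothing can infer embolization. The MRI's own contribution therefore falls mainly on subjects who improved, in either arm.

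At stake is whether a 6-month difference can be read as an effect of embolization rather than partly as an effect of knowing the arm.

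**Working it through.** **1. Order of events.** The 1-month visit is at 30 ± 7 days and the 6-month visit at 180 ± 10 days, a nominal gap of 180 − 30 = 150 days. The scheduled MRI and the unblinding rule both act at or just after 1 month, so the 3- and 6-month scores follow them. The 1-month scores are less exposed: Section 3.1 puts the scan after the visit, and Section 6.5 mentions the questionnaires before the scan but fixes no order and does not say when the scan is booked.

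**2. Who is scanned on schedule.** With N = 21 at 2:1, the planned arms are 14 GAE and 7 sham. Before crossover the schedule gives a post-procedure MRI to 14 of 14 and 0 of 7.

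**3. The plan's own power (Section 8.1).** One-sided two-sample t-test, alpha 0.05, n = 14 and 7, df = 19, critical value 1.729, noncentrality = (difference / SD) × √(14 × 7 / 21) = (difference / SD) × 2.160.

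- WOMAC: difference 0.16 × 12.2 = 1.952; 1.952 / 1.9 = 1.027; noncentrality 2.219; power 68.9% (stated 69.1%).
- VAS: difference 0.15 × 72 = 10.8; 10.8 / 13.3 = 0.812; noncentrality 1.754; power 51.9% (stated 51.7%).

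Both reproduce closely, so the same test is a fair basis for illustration.

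**4. Illustrative effect of lost blinding.** The documents give no figure for expectation bias, so the shift is an assumption. With no true effect and a VAS shift toward GAE, SD 13.3:

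| Assumed shift (mm) | Noncentrality | Rejection at nominal 5% |
|---|---|---|
| 1 | 0.162 | 6.8% |
| 2 | 0.325 | 9.2% |
| 3 | 0.487 | 12.0% |
| 4 | 0.650 | 15.4% |
| 5 | 0.812 | 19.4% |

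With an assumed SD of 20 to 25, shifts of 3 to 5 mm give about 8% to 13%. All these shifts are less than half of the 10.8 mm relevant difference.

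**5. Does the planned model's 1-month contrast give a blinded estimate?** It does not. Section 8.2 fits scores at 0, 1, 3 and 6 months as linear in time. For complete data with an arm-specific intercept and slope, the mean time is 10 / 4 = 2.5 and the sum of squares is 21. The weight of visit t in the fitted 1-month mean is 1/4 + (1 − 2.5)(t − 2.5) / 21:

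- baseline: 0.25 + 3.75 / 21 = 0.43
- 1 month: 0.25 + 2.25 / 21 = 0.36
- 3 months: 0.25 − 0.75 / 21 = 0.21
- 6 months: 0.25 − 5.25 / 21 = 0

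The weights were unchanged under the random-intercept-and-slope covariances tried. About a fifth of that contrast would come from a visit after the MRI. An effect that is constant from 1 month onward would appear at 0.36 + 0.21 = 57% of its size.

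**The case against.** **Disclosure is inferred.** A scan identifies the arm only to a subject who knows that the other arm is not scanned. The consent pages and the flow chart are not in the reviewed text, and every subject has had a knee MRI at or before screening. This stands: a reader might infer that allocation is revealed to everyone, but the documents support only that it may be. They also plan nothing to prevent it.

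**The MRI is not the only source.** Non-improving sham subjects are unblinded by design. This stands too: a reader might attribute the whole loss of blinding to the scan, and that would be wrong. The scan extends possible disclosure to subjects whom the rule does not reach.

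**Other MRIs occur.** Scans prompted by adverse events are possible in either arm, so it would be wrong to say that sham subjects are never scanned. Occasional unscheduled scans would not hide a scan given to one whole arm.

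**The 1-month scores may be compromised as well.** This reading is weak. Section 3.1 and the order of the text in Section 6.5 both point to scores first; only the time of booking is left open.

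**The error rates are hypothetical.** They are: the shift has no source in the documents, and the planned analysis is a model-based Wald test, not a simple t-test.

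**Conclusion.** The concern holds as a risk, not as an established loss of blinding. By 6 months, an arm-dependent MRI and an arm-dependent unblinding rule have both operated, the tested outcomes are self-reported, and the documents neither mask the schedule nor check blinding. Sections 6.6 and 6.8 nevertheless call these subjects blinded. Those titles and Section 5.5 need to be reconciled with Sections 3.1, 5.2 and 6.5.

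The size of any bias is unknown. The range of about 7% to 19% rests on an assumed VAS shift of 1 to 5 mm, SD 13.3, full enrolment of 14 and 7, and a simple t-test. It shows sensitivity and does not estimate this trial's error rate. Nor does it separate the MRI's share from that of the 1-month rule.

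**What to change.** No additional MRI is needed.

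1. In Section 6.5, state that the 1-month WOMAC, VAS and a question on which procedure the subject believes they had are completed before the MRI is booked or mentioned and before any arm is revealed. Reconcile Sections 3.1 and 6.5 on when the scan takes place.
2. In Section 8.2, add a baseline-adjusted GAE versus sham comparison of the observed 1-month scores, or a categorical-time model using only baseline and 1-month data, as the blinded comparison. Do not use the 1-month contrast from the linear-in-time model. Label the comparison a pre-specified supportive analysis, so that the single 6-month test per endpoint, and the plan's reason for not adjusting for multiplicity, are unchanged.
3. Describe the 6-month result as not reliably blinded, and report the treatment-guess answers by arm.

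The cost is wording on visit order, one question and one short analysis. The drawback is that the blinded answer is short-term and supportive only; the 6-month comparison stays exposed.

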6.6 Visit 6a and 6b - 3 Month Follow-Up for blinded subjects

Subjects will be seen in clinic or contacted by phone or by teleconference, per the subject's preference, 90 +/- 10 days following GAE or sham procedure. The WOMAC questionnaire and VAS pain score will be completed and subjects will be evaluated for possible adverse events. Subjects will also provide an update about the necessity/frequency of pre-established conservative therapies. If an AE is suspected based on change in pain scores or functionality, an appropriate

work-up will be performed which may include MRI.

6.7 Visit 6c - GAE for unblinded subjects

GAE will be performed (as described in part 5.2 above) within 4 weeks of visit 4. Subjects will be given a pager number to reach a physician, 24 hours a day, to report any adverse symptoms and receive medical advice.

6.8 Visit 7a and 7b - 6 Month Follow-Up for blinded subjects

Subjects will be seen in clinic or contacted by phone or by teleconference, per the subject's preference, 180 +/- 10 days following GAE or sham procedure. The WOMAC questionnaire and VAS pain score will be completed and subjects will be evaluated for possible adverse events. Subjects will also provide an update about the necessity/frequency of pre-established conservative therapies. If an AE is suspected based on change in pain scores or functionality, an appropriate work-up will be performed which may include MRI.

6.9 Visit 7c - 1 day follow-up for unblinded subjects

Subjects will be seen in clinic or contacted by phone or by teleconference, per the subject's preference, the day following GAE (+3 days). As most complications of the procedure will be evident within this time period, this visit is to evaluate for early AE's. If an AE is suspected based on change in pain scores or functionality, an appropriate work-up will be performed which may include MRI.

6.10 Visit 8c – 2 Week Follow-Up for unblinded subjects (arm C only) Patients will be called after 2 weeks to assess any adverse events, such as persistent pain.

6.11 Visit 9c-1 month follow-up for unblinded subjects

Subjects will be seen in clinic 30 +/- 7 days following GAE. The WOMAC questionnaire and VAS pain score will be completed and subjects will be evaluated for possible adverse events. An MRI of the treated knee will be acquired. Subjects will also provide an update about the necessity/frequency of pre-established conservative therapies.

6.12 Visit 10c- 3 month follow-up for unblinded subjects

Subjects will be seen in clinic or contacted by phone or by teleconference, per the subject's preference, 90 +/- 10 days following GAE. The WOMAC questionnaire and VAS pain score will be completed and subjects will be evaluated for possible adverse events. Subjects will also provide an update about the necessity/frequency of pre-established conservative therapies. If an AE is suspected based on change in pain scores or functionality, an appropriate work-up will be performed which may include MRI.

6.13 Visit 11c - 6 month follow-up for unblinded subjects

[figure not shown]
Subjects will be seen in clinic or contacted by phone or by teleconference per, the subject's preference, 180 +/- 10 days following GAE. The WOMAC

questionnaire and VAS pain score will be completed and subjects will be evaluated for possible adverse events. Subjects will also provide an update about the necessity/frequency of pre-established conservative therapies. If an AE is suspected based on change in pain scores or functionality, an appropriate work-up will be performed which may include MRI.

6.14 Visit 8a, 8b, or 12c-12 month follow-up for all subjects

Subjects will be seen in clinic or contacted by phone or by teleconference per, the subject's preference, 180 +/- 10 days following GAE. The WOMAC questionnaire and VAS pain score will be completed and subjects will be evaluated for possible adverse events. Subjects will also provide an update about the necessity/frequency of pre-established conservative therapies. If an AE is suspected based on change in pain scores or functionality, an appropriate work-up will be performed which may include MRI.

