3.3 Secondary Study Endpoints

1. Reduction of previously initiated OA medical therapy (e.g. NSAIDs) at 12 months follow-up.

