We will identify extreme primary endpoint values by computing studentized residuals and then conduct sensitivity analyses by deleting these outliers from the analysis datasets. We will repeat the above statistical tests and use results of the sensitivity analyses to corroborate conclusions reached in the primary analyses.

We will address the secondary study endpoint of reduction of OA by comparing frequency of OA medical therapy between the sham group, the crossover group, and the GAE group at 12 months. We will employ a chi-squared test to test the H_0 : frequency of OA medical therapy is equal for between the sham group, the crossover group, and the GAE group versus the one-sided alternative hypothesis. A p-value of < 0.05 will be taken as evidence to suggest that the frequency of OA medical between the groups. Non-significance of the p-value for this test will be considered inconclusive evidence against the null hypothesis.

Reduction in AE will be evaluated with a multilevel logistic regression model. The outcome of adverse events will be regressed on treatment status. We will employ a compound symmetric R-side covariance structure to account for dependencies arising from observations from the same patient. The H_0 : frequency of AE is equal for between the sham group and the GAE group will be assessed versus the two-sided alternative hypothesis with a statistical test of the treatment

parameter different than 0, with a p-value of < 0.05 taken as evidence to suggest that the frequency of OA medical therapy is not equal between the groups. Non-significance of the p-value for this test will be considered inconclusive evidence against the null hypothesis.

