8.3 Subject Population(s) for Analysis

A patient will be considered an evaluable study subject evaluable for data analysis per the following criteria, a written informed consent was obtained, he/she meets the inclusion and exclusion criteria, and received the GAE or sham study procedure. All subjects with 12 month followup data will be included for analysis even if some follow up data is incomplete. Every attempt will be made to ensure that there is as little missing data as possible including reminder phone calls and follow-up phone calls, if a subject misses a visit.

9 Risk Analysis

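### Section 6.14 puts the 12-month visit in the 6-month window and counts it only from GAE, leaving sham-only subjects without a start date

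*Combined protocol and SAP*

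**What the plan says.** The heading of 6.14 reads "Visit 8a, 8b, or 12c-12 month follow-up for all subjects". The sentence beneath it sets the timing at "180 +/- 10 days following GAE". At this visit subjects complete WOMAC and VAS and report their use of existing conservative therapies.

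The 6-month visit for blinded subjects (6.8) is set at "180 +/- 10 days following GAE or sham procedure". The 6-month visit for crossover subjects (6.13) has the same 180-day target and 10-day tolerance, counted from GAE.

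Other sections treat month 12 as a time point of its own:

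- 3.1 lists "follow-up visits at 24 hours, 2 weeks, 1, 3, 6, & 12 months".
- 6.5 says that crossover subjects are "followed at similar follow-up intervals to 12 months".
- 3.3 gives the only secondary endpoint as "Reduction of previously initiated OA medical therapy (e.g. NSAIDs) at 12 months follow-up".
- 8.2 analyses that endpoint by "comparing frequency of OA medical therapy between the sham group, the crossover group, and the GAE group at 12 months".
- 8.3 adds that "All subjects with 12 month followup data will be included for analysis even if some follow up data is incomplete".

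**The concern.** There are two separate faults in one sentence.

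The first is the window. A visit labelled 12 months carries the 6-month day count. Staff who follow the text would record medication use at about six months a second time. Staff who follow the heading would find no stated tolerance around month 12. The trial runs at two centres (11.1.1), so the two could resolve this differently.

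The second is the start date. The section covers all subjects, but the count begins at GAE. A sham subject who never crosses over has no GAE, so the visit date cannot be worked out. Changing the day count alone would leave this fault in place.

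What is at stake is the secondary endpoint. The therapy update taken at this visit is the natural source for the three-group comparison at 12 months, and no other visible section gives that visit a window.

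**Working it through.** **Inputs.** Follow-up targets and tolerances: 30 +/- 7 days (6.5), 90 +/- 10 (6.6), 180 +/- 10 (6.8 and 6.13), 180 +/- 10 (6.14). Sample size 21, randomised 2:1 GAE to sham (3.1).

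**Step 1: the windows.**

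| Visit | Section | Label | Window | Counted from |
|---|---|---|---|---|
| 7a, 7b | 6.8 | 6 months | 180 - 10 = 170 to 180 + 10 = 190 | GAE or sham |
| 11c | 6.13 | 6 months | 170 to 190 | GAE |
| 8a, 8b, 12c | 6.14 | 12 months | 170 to 190 | GAE only |

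Each window holds 190 - 170 + 1 = 21 days. For subjects whose visits are counted from GAE, all 21 days coincide.

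**Step 2: distance from month 12.** The documents give no day number for month 12, so two conventions are shown.

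- The protocol's other targets imply 30-day months (30/1 = 90/3 = 180/6 = 30), so month 12 would be day 12 x 30 = 360. The 6.14 window closes 360 - 190 = 170 days earlier and opens 360 - 170 = 190 days earlier.
- On a 365-day year it closes 365 - 190 = 175 days earlier and opens 365 - 170 = 195 days earlier.

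The shortfall from the end of the window is therefore 170 to 175 days, which no tolerance used elsewhere in the schedule could cover.

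**Step 3: subjects without a start date.** With 2:1 allocation, the sham arm has 21 x 1/3 = 7 subjects. A sham subject who crosses over acquires a GAE date, so the number with no start date is 7 minus the crossovers. Seven is the maximum and applies only if nobody crosses over. For the GAE arm and for crossover subjects, the start date is clear.

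That visit 8b belongs to the sham arm is an inference from the lettering. The point does not depend on it, because the heading of 6.14 covers all subjects.

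**Step 4: likely origin.** The timing sentence in 6.14 repeats the one in 6.13, where both 180 days and a GAE start are consistent with the visit's label. Copying that sentence into 6.14 would explain both faults together.

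**Step 5: what depends on it.** The primary comparison in 8.2 is a predicted difference at 6 months, from scores collected at baseline and at 1, 3 and 6 months. The power statement in 8.1 does not use month 12. Neither changes when 6.14 is corrected. The comparison of OA therapy at month 12 (3.3 and 8.2) does depend on this visit.

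**The case against.** The strongest reply is that nobody running the trial would be misled for long. The heading of 6.14, the visit list in 3.1, the endpoint in 3.3, the crossover follow-up in 6.5 and the analysis in 8.2 all point to a real 12-month visit. The 180-day visit already exists under other visit numbers, so a literal reading would put two numbered visits in one window. The flow chart in 6.15 and the schema in table 1 cannot be seen here, and either may give the correct window and start date.

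Much of this stands. A reader might infer that no subject would have a 12-month visit and that the secondary endpoint would be lost. The documents do not support that, because it requires sites to disregard the heading and every other section that names month 12. The realistic risk is inconsistent timing and an undefined window.

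What does not stand is the idea that the unseen chart settles the matter. Even if it is correct, the text of 6.14 still contradicts its own heading, and sites would hold two rules.

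A reader might also take the sentence in 8.3 about 12-month data as limiting the 6-month analysis to those who complete month 12. That is not its ordinary sense. It does not say that only such subjects are included, the sentence before it sets no follow-up condition, and 4.7.2 keeps the recorded data of subjects who withdraw.

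**Conclusion.** The point holds as an internal inconsistency in the visit schedule. In 6.14 the window duplicates the 6-month visit, closes 170 to 175 days short of month 12, and has no start date for sham-only subjects, who number at most 7 of 21. The day count and the missing start date are read directly from the text. The shortfall rests on taking month 12 as day 360 or 365, and the upper limit of 7 on exact 2:1 allocation with no crossover.

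It should be corrected because it is an operative visit rule for the only secondary endpoint, and no other visible text supplies that rule. Its reach is limited to the 12-month data. The wording of 8.3 merits a clarifying note and is not an established flaw in the analysis population.

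**What to change.** Reconcile the window and the start date in 6.14 with its heading and with 3.1, 3.3, 6.5 and 6.8, separately for visits 8a, 8b and 12c, so that every subject, including sham subjects who do not cross over, has a date from which the visit is counted. Check the result against the 6.15 flow chart and the table 1 schema so that all three agree.

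As a wording note only, the second sentence of 8.3 could add that treated subjects without 12-month data still enter the 6-month models, in line with 4.7.2.

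The cost is one corrected sentence in 6.14 and, optionally, one clarified sentence in 8.3. No extra subjects, visits or measurements beyond those already planned are needed.
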